#### 6.1.6. Suspected unexpected serious adverse reactions

A suspected unexpected serious adverse reaction (SUSAR) is an unexpected adverse drug reaction which also meets the definition of serious adverse events.

#### 6.2. Methods of recording and assessing adverse events

Patients will be kept for observation for at least 3 hours following each morning treatment for any acute AEs. During the reporting period, any unfavorable changes in the subject's condition will be recorded as adverse events, whether reported by the subject or observed by the investigator. In case of any abnormal finding, the local study physician will perform a full clinical examination and findings will be recorded. An emergency kit will be available on site to treat any medical conditions that warrant urgent medical intervention.

In addition, patients will be also interviewed by a nurse and/or a physician about the occurrence of AEs 24 hours after treatment.

Information on all AEs (onset, duration, intensity, seriousness and causality) will be immediately entered in the appropriate AE module of the CRF which is considered as a source document. For all AEs, sufficient information will be pursued and/or obtained so as to permit i) an adequate determination of the seriousness of the event (i.e. whether the event should be classified as a SAE); ii) an assessment of the casual relationship between the AE and the study treatments (i.e. whether the event should be classified as an adverse drug reaction); and iii) an assessment of intensity of AEs by the study physician.

All SAE, unexpected adverse drug reactions, or SUSARs must be reported as described in Section 6.3.

#### 6.3. Reporting of serious adverse events

Any study-related unanticipated problem posing risk of harm to subjects or others, and any type of serious adverse event, will be reported (within 24h between site's knowledge about the event and notification) to

[name]. [name] (principal investigator) Swiss Tropical and Public Health Institute, [contact] [contact] E-mail: [contact]

Page 30 of 45

Within the following 48 hours, the local co-investigator must provide to study sponsorinvestigator further information on the serious adverse effect or the unanticipated problem in the form of a written narrative. This should include a copy of a completed SAE form, and any other diagnostic information that will assist the understanding of the event. In exceptional circumstances, a serious adverse event may be reported by telephone. In these cases, a written report must be sent immediately thereafter by fax or e-mail. Names, addresses and telephone for serious adverse event reporting will be included in the trial-specific SAE form. Relevant pages from the CRF may be provided in parallel (e.g., medical history, concomitant medications).

#### 6.4. Safety reporting to Health Authorities and Ethics Committees

The sponsor-investigator will send appropriate safety notifications to Health Authorities in accordance with applicable laws and regulations. Additionally, this information will be provided to the 'Ethik Kommission Nordwest- und Zentralschweiz' (EKNZ, Switzerland) and the ethic committee of Lao PDR according to national rules. Fatal or life-threatening serious adverse events or SUSARs will be reported within 24 hours (between sponsor-investigator's knowledge about the event and notification) followed by a complete report within 7 additional calendar days. Other serious adverse events and SUSARs that are not fatal or life-threatening will be filed as soon as possible but no later than 14 days after first knowledge by the sponsor-investigator.

# 7. Statistics

#### 7.1. Definition of primary endpoint

Cure rate is the primary outcome measure of our study.

#### 7.2. Justification of number of trial subject

(A) DF study: Since it is already known that moxidectin acts on S. stercoralis and the existence of a drug effect is known, the main aim of the study is the elucidation of the nature of the dose-response relationship. Computer simulations showed that with 30 adults enrolled in each of the 7 study arms (0, 2, 4, 6, 8, 10, 12 mg) the dose response prediction model had a median precision (one half length of the 95%-confidence intervals) of 9%-points assuming associated true cure rates of 2.5%, 30%, 55%, 75% and 85%,

90%, 95% and a loss to follow up of 10%. The sample size is also in line with the recommendations from *Klingenberg et al. 2009* [38].

*DF study - PK sampling*: The suggested sample size of 15 participants per study arm is sufficiently high to determine the key PK parameters, considering that PK variability is low. A low PK variability is a reasonable assumption when dealing with adults.

(B) Non-inferiority moxidectin versus ivermectin: The main hypothesis of this trial is that an 8 mg dose of moxidectin is non-inferior against *S. stercoralis* compared to the standard of care therapy (ivermectin). We assume a similar true CRs for moxidectin and ivermectin of 89% [15]. The sample size determination revealed, that we need 154 participants in each trial arm to demonstrate non-inferiority of moxidectin with a non-inferiority margin of 10%-points with 80 power at the 95% confidence interval (equivalent to the 97.5% lower confidence bound). To account for an expected loss to follow-up of 10%, we target to enroll 175+175 = 350 participants.

#### 7.3. Description of statistical methods

An available case analysis (full analysis set according to the intention to treat principle) will be performed, including all subjects with primary end point data. Supplementary, a per-protocol analysis will be conducted. CRs will be calculated as the percentage of worm-positive adults at baseline who become worm-negative after treatment. LPG will be assessed by calculating the mean of the larvae counts from the three duplicate Baermann assays and relate this value to the mean weighted amount of stool sample. The LRR will be calculated (LRR = (1-(mean at follow-up/mean at baseline))\*100).

AEs will be evaluated descriptively as the difference of proportion reporting adverse events before and after treatment.

Trial A:  $E_{max}$  models using the Dose Finding package of the statistical software environment R will be implemented to predict the dose-response curves in terms of CRs and LRRs. Noncompartmental and nonlinear mixed-effects (NLME) modeling will be used to determine pharmacokinetic parameters.

On the basis of the LC-MS/MS measurements, the following PK parameters for plasma, whole blood and capillary blood will be calculated:

• Cmax maximal plasma concentration

- tmax time to reach Cmax
- AUC area under the curve, from 0 to 24h and 0 to inf.
- t1/2 elimination half-life

 $C_{max}$  and  $t_{max}$  will be observed values derived from the plasma concentration time profile. AUC and  $t_{1/2}$  will calculated with the software WinNonlin (Version 5.2, Pharsight Corporation, USA) using compartmental analysis. The elimination half-life will be estimated by the equation:  $t_{1/2} = ln2/\lambda$ , where  $\lambda$  will be determined by performing a regression of the natural logarithm of the concentration values during the elimination period.

Trial B: The non-inferiority margin is set to 10%-points, i.e. if the lower bound of the 95% CI of the differences in cure rates is greater than -0.1 we conclude that moxidectin is non-inferior to ivermectin. The 95% confidence interval of the differences in CRs will be estimated using the standard formula:

 $CI = (CR_{mox} - CR_{iver}) + - Z_{a/2} * \sqrt{(SE_{mox}^2 + SE_{iver}^2)}.$ 

Questionnaires on physical functioning and treatment satisfaction will be evaluated by creating summary scores by summing up and transforming the single question scores according to the following formula: [(actual raw score-lowest possible raw score)/(possible raw score range)]\*100 [39].

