## IV. Synopsis

Study Title	Efficacy, safety and pharmacokinetics of ascending dosages of moxidectin alone and in comparison to ivermectin against Strongyloides stercoralis infection in adults: a randomized controlled trial	
Study Type	Phase 2 trials – Phase 2a (trial A) & Phase 2b/3 (trial B)	
Sample size	210 (trial A) and 350 (trial B) in two settings	
Indication	Strongyloidiasis stercoralis infection (larvae in stool)	
Investigational Product and Reference Treatment	Investigational product: moxidectin Reference treatment: ivermectin	
Protocol Number, Date and Version	2, 01.07.2020, v2.2	
Trial registration	Will be registered on ( http://www.controlled-trials.com/ )	
Study Rationale	
 
To provide evidence on:
 
(A) Effective doses and safety of moxidectin in adults against infection with S. stercoralis in Laos (trial A: dose finding study).
 
(B) Efficacy and safety of moxidectin compared to ivermectin in adults against infection with S. stercoralis in Laos and Cambodia (trial B: parallel group study).
 
	
Study Objectives	
 
To determine the efficacy and safety of:
 
a) seven ascending oral moxidectin dosages in adults infected with S. stercoralis, namely placebo, 2 mg, 4 mg, 6 mg, 8 mg, 10 mg, 12 mg and to measure moxidectin disposition in adults using a microsampling device.
 
b) the recommended dose moxidectin (i.e. the most promising dosage identified in trial A; 8 mg) in comparison to the standard treatment dose of ivermectin (200 μg/kg) in adults infected with S. stercoralis.
 
Our primary objective is to determine the dose-response of
 
	
	
 
moxidectin based on cure rates (CR) against S. stercoralis and to quantify the efficacy of the recommended dose to the standard treatment (ivermectin) in adults:
 
a) in a dose finding study
 
placebo, 2 mg, 4 mg, 6 mg, 8 mg, 10 mg and 12 mg moxidectin
 
b) in a parallel group trial
 
	

	1	
	8 mg moxidectin (absolute value depends on results of (A)), and 200 $\mu$ g/kg ivermectin.	
	The secondary objectives of the trial are:	
	
 
to evaluate the safety and tolerability of the dose- dependent treatment regimes.
 
	
	
 
to evaluate the safety and tolerability of moxidectin compared to ivermectin.
 
	

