Measurements & procedures	Three stool samples will be collected at baseline if possible on three consecutive days or otherwise within a total maximum of 6 days and analysed by a quantitative Baermann method (in duplicates) for S. stercoralis infection. Co-infection with T. trichiura, A. lumbricoides and hookworm infection will be identified using duplicate Kato-Katz thick smears on stool samples from two consecutive days. The medical history of the participants will be assessed with a standardized questionnaire, in addition to a clinical and physical examination carried out by the study physician shortly before treatment day. The adults will also be interviewed before treatment, 3 and 24 hours as well as 28 days after treatment about the occurrence of AEs. The efficacy of the treatment will be determined 21-28 days post-treatment by collecting another three stool samples. All stool samples will be examined with duplicate Baermann assays and Kato-Katz thick smears and recorded quantitatively. A subsample of adults will further be sampled using finger pricking for micro sampling at 0, 2, 4, 8, 24, and 72 hours, 7 and 28 days post treatment to evaluate pharmacokinetic parameters (trial A). For validation of the analytical method the subsample of one study arm (8 mg, trial A) will undergo venous blood sampling in addition to finger pricking. To all participating households, a brief questionnaire will be administered assessing information on socioeconomic characteristics (possession of indicator assets) and access to sanitation, water facilities, and hygiene behaviour at first visit. Additionally, soil and water samples at different sites will be taken.
Statistical Analyses	An available case analysis (full analysis set according to the intention to treat principle) will be performed, including all subjects with primary end point data. Supplementary, a per-protocol analysis will be conducted. CRs will be calculated as the percentage of larvae-positive subjects at baseline who become larvae-negative after treatment. Larvae per gram (LPG) stool sample will be assessed by calculating the mean of the larvae counts from the three duplicate Baermann assays and divided by the mean weighted amount of these stool samples. The LRR will

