#### The secondary study objectives are

- 1.) To compare the efficacy based on larvae reduction rates of ascending oral moxidectin dosages in a total of 210 adults infected with *S. stercoralis*.
- 2.) To determine safety & tolerability of ascending oral moxidectin dosages in a total of 210 adults infected with *S. stercoralis*.
- 3.) To comparatively assess the efficacy based on larvae reduction rates moxidectin versus ivermectin (200 μg/kg), the current drug of choice, against *S. stercoralis* in 350 adults infected with *S. stercoralis*.
- 4.) To determine safety & tolerability of moxidectin versus ivermectin (200 μg/kg), the current drug of choice, against *S. stercoralis* in 350 adults in two countries infected with *S. stercoralis*.
- 5.) To determine pharmacokinetic parameters in 10 adults infected with *S. stercoralis*, after oral moxidectin administration of 8 mg, using venous as well as capillary blood allowing the validation of the micro sampling analysis to measure moxidectin blood levels.
- 6.) To measure moxidectin deposition and determine exposure (including Cmax, AUC and tmax)response correlation using a microsampling technology after oral moxidectin administration of 2 mg, 4 mg, 6 mg, 8 mg, 10 mg, 12 mg versus placebo in a total of 90 adults infected with *S. stercoralis*.
- 7.) To determine the population PK parameters of the optimal dose of moxidectin in the treatment of *S. stercoralis.*

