#### 4.3.2. Physical and clinical examination

At baseline, the medical history of *S. stercoralis*-infected participants in the study will be assessed with a clinical and physical examination carried out by the study clinician, who will assess weight, height, body temperature, pulse rate, blood pressure. Hemoglobin (Hb) levels will be detected using HemoCue to exclude severely anemic participants (below 80 g/l in adults according WHO) [31]. To avoid accidental treatment of pregnant women all female participants will be asked to provide a urine sample of at least 10 ml to be subjected to a pregnancy RDT. Women will be individually counselled that they should not become pregnant during the entire study period and will be interviewed if they are currently breastfeeding or planning to become pregnant. Any symptoms and abnormalities prior to treatment will be recorded on the case report form (CRF).

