#### 4.3.3. Adverse effects assessment

All participants will be kept for observation for at least 3 hours following each morning treatment for any acute adverse events and additionally will be interviewed and examined about existing and emerging clinical symptoms (i.e. headache, abdominal pain, itching, nausea, vomiting, diarrhea, body temperature, and allergic reaction) before treatment (baseline examination), 3 hours, 24 hours and 28 days after treatment (adverse effects assessment) to determine the occurrence of AE (see chapter 6.2). Any symptoms will be recorded in the CRF and immediate action will be perused (see chapter 6).

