## 4.6. Schedule of visits

Table 1. Schedule of visits of DF (trial A) and parallel group (trial B) study.

Screening /					Follow up		
Time point	Day -28	Day -1-3	0 h	л	3 h	24 h	Day 28
Informed consent	х			ando			
Diagnosis (stool examination) (a)	х			Randomization			х
Questionnaire	х			on and			
Medical history (c)		х					
Clinical examination (d)		Х		ninistr			
Physical examination (e)		х		administration of			
Randomization administration of treatment			х				
Capturing AEs (f)				treatment	х	Х	х
Capturing SAE (f)				1t	х	х	х

(a) on three stool samples duplicate Baermann assays and on two stool samples duplicate Kato-Katz thick smears. (b) date of birth, age, sex, height, weight, body temperature, pulse rate, blood pressure, hb measurement, pregnancy test and recording of breastfeeding

(c) information gained by asking specific questions concerning chronic disease and concomitant medication.

(d) investigation for signs of disease: head ache, abdominal pain, nausea, vomiting, diarrhea, itching, other symptoms. (e) examination on ear, nose, throat, eyes, lungs, lymph nodes and skin.

(f) a standardized symptom questionnaire is used, that includes the recording of headache, abdominal pain, itching, nausea, vomiting, diarrhea, allergic reaction, others

(g) only in trial B

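### The only adverse-event summary in section 7.3 subtracts a pre-treatment proportion, which conflicts with the protocol's own AE definition, can mask new events within an arm, and states no moxidectin-versus-ivermectin statistic for trial B

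*Combined protocol and SAP*

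**What the plan says.** Section 7.3 has a single sentence on AE analysis: "AEs will be evaluated descriptively as the difference of proportion reporting adverse events before and after treatment". It does not say what is counted before treatment, which post-treatment assessment or assessments form the after count, or whether results are given by arm. The statistics text of the Synopsis, as far as it can be read, adds nothing on AEs.

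The AE definition is elsewhere. Sections 6.1 and 6.1.2 start AE observation when treatment starts, and 6.1.2 runs it to day 28. Section 6.1.1 treats conditions already present at the first visit as baseline conditions, not AEs, unless they worsen in severity or frequency.

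Symptoms are nevertheless collected before treatment. The Synopsis says: "The adults will also be interviewed before treatment, 3 and 24 hours as well as 28 days after treatment about the occurrence of AEs". Section 4.3.3 gives the times as "before treatment (baseline examination), 3 hours, 24 hours and 28 days after treatment (adverse effects assessment) to determine the occurrence of AE". Section 4.3.2 has pre-treatment symptoms entered on the case report form. The notes to Table 1 (section 4.6) show nearly the same symptom list on both sides of dosing. Note (d), before treatment, reads "investigation for signs of disease: head ache, abdominal pain, nausea, vomiting, diarrhea, itching, other symptoms"; note (f), for AE capture, reads "a standardized symptom questionnaire is used, that includes the recording of headache, abdominal pain, itching, nausea, vomiting, diarrhea, allergic reaction, others".

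The trial B safety objective is comparative. The Synopsis has "to evaluate the safety and tolerability of moxidectin compared to ivermectin", and objective 4 in section 3 begins "To determine safety & tolerability of moxidectin versus ivermectin". Section 4.1 makes safety a secondary endpoint.

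**The concern.** Under the AE definition in section 6 nothing can be an AE before treatment, so a before proportion of AEs has no content of its own. The pre-treatment interview does supply a number, namely baseline symptom prevalence. Because the Synopsis and 4.3.3 place that interview under the occurrence of AEs, an analyst following 7.3 would most naturally subtract it.

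The result is then a net change in symptom prevalence and not a measure of harm. A headache that clears offsets a new one in someone else, and worsening in a person already symptomatic does not register, although 6.1.1 counts it as an AE. A near-zero or negative figure could be reported for an arm in which new events occurred. In addition, a within-arm change is not a comparison of moxidectin with ivermectin, so the trial B safety objective has no stated statistic.

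**Working it through.** The documents contain no AE figure to reproduce. The check has a textual part and an arithmetical part in which every rate is an assumption.

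**1. The two readings of the before term.**
- Section 6 definition applied strictly: before is zero, and the difference is simply the post-treatment proportion. The subtraction is redundant but harmless.
- Pre-treatment interview used: before is baseline symptom prevalence.

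If 20% report symptoms after treatment, the statistic is +20 points when before is zero. It is +10, 0 or -20 points when baseline prevalence is 10%, 20% or 40% (20-10, 20-20, 20-40).

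**2. What the second reading does within an arm.** Let b be baseline prevalence of any symptom, q the probability that a baseline symptom resolves, and e the risk of a new or worsened event. Assume e is independent of baseline status and of resolution.

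After = (1-b)e + b[(1-q) + qe]

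Change = After - b = (1-b)e - bq(1-e)

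At b = 30%, q = 50%:
- e = 20%: 0.70×0.20 - 0.30×0.50×0.80 = 0.14 - 0.12 = +2.0 points
- e = 10%: 0.70×0.10 - 0.30×0.50×0.90 = 0.07 - 0.135 = -6.5 points

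The change is zero or negative once q ≥ [e/(1-e)] / [b/(1-b)]:

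| e | b = 10% | b = 30% | b = 50% |
|---|---|---|---|
| 10% | 1.00 | 0.26 | 0.11 |
| 20% | above 1 (never) | 0.58 | 0.25 |

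If b is below e the change is never negative. Over b = 10–50% and q = 25–75% it runs from +16.0 to -20.0 points at e = 20%, and from +6.75 to -28.75 at e = 10%.

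**3. What it does between arms.** With the same b and q in both arms, as randomisation makes reasonable for b, Gap = (e1-e2)[1-b(1-q)]. The gap is attenuated but keeps its sign. In the example it is 10×(1-0.15) = 8.5 points instead of 10; over the same grid it is 6.25 to 9.75.

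Per symptom, with b = 5% and risks of 5% versus 2.5%, the gap is 2.41, 2.44 and 2.47 at q = 25%, 50% and 75%, against a true 2.5. The lower-risk arm's own change still runs +1.2, -0.1, -1.3.

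If 6.1.1 is applied to the after count, so that unchanged symptoms are dropped there but still counted before, the change is e - b. At b = 30% that is -10 and -20 points for e = 20% and 10%. The gap is then exactly 10.

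**4. Unequal assessment.** Section 4.3.3 has one assessment before treatment and three after. If after means any report at 3 h, 24 h or day 28, the extra opportunities push the difference upward, and q becomes the chance that a baseline symptom is absent at all three visits. This works against the downward pull in step 2, so the net direction cannot be predicted.

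**5. Precision of a trial B difference.** Half-width = 1.96×√[2p(1-p)/n], with p an assumed AE proportion in both arms:

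| p | n = 175 per arm (enrolled) | n = 154 per arm (required number in 7.2) |
|---|---|---|
| 10% | 6.3 points | 6.7 points |
| 20% | 8.4 points | 8.9 points |
| 30% | 9.6 points | 10.2 points |

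**The case against.** The strongest reply is that little comparative harm follows. Trial B is randomised and double blind, so baseline symptoms should be similar across arms and subtracting them is a recognisable baseline adjustment. Symptoms are elicited by name and section 10.1 records AEs by number and type, so a per-symptom table is likely, and there the gap barely moves. Section 7.3 calls the analysis descriptive, the objectives promise no interval, and by-arm proportions set next to each other would give a comparison. Onset, intensity, seriousness and causality are recorded for each AE (6.2), so new events can be derived at analysis. Finally, b, q and e are all assumed.

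Most of this stands. A reader might infer that the rule biases the moxidectin-versus-ivermectin comparison materially or favours one drug; the documents do not support that, and step 3 points to attenuation that is usually small. A reader might also infer that no safety comparison will be made. By-arm description is not excluded, and its absence from the text would by itself be only missing detail. Nor is cure rate the only outcome that 7.3 examines across arms: that holds for trial B, whereas in trial A both cure rate and larvae reduction rate are modelled across doses.

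What does not fall away is the rule itself. The one statistic named in 7.3 is within-arm, is at odds with section 6 on its natural reading, and can be zero or negative while events occur. Keeping the randomisation codes back until final data release (4.4) limits later choice of the summary but does not define it.

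**Conclusion.** The concern holds for the within-arm statistic and should be corrected. That 7.3 contains one AE rule, that its natural reading conflicts with 6.1 to 6.1.2, and that no trial B AE contrast is stated are matters of text and are certain. The size and direction of the within-arm distortion are unknown, because the documents give no baseline prevalence, resolution share or event rate. The figures above show only what is possible, under independence and a pooled any-symptom measure, and they leave out the upward push from three assessments against one. Distortion of the between-arm gap is probably small, and is absent if unchanged baseline symptoms are left out of the after count. On the reading where before is zero, the sentence is redundant and does no harm. Safety is a secondary endpoint; the primary non-inferiority conclusion and the sample size are unaffected.

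**What to change.** Replace the AE sentence in 7.3 with the following.

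- For each arm, report the number and proportion of treated participants with at least one new or worsened event relative to the baseline record, over the whole period from treatment to day 28 and separately at 3 h, 24 h and day 28.
- Tabulate baseline symptoms separately, without subtracting them.
- For trial B, add the moxidectin-minus-ivermectin difference in that proportion with a 95% CI, labelled descriptive and without a formal test.
- For trial A, tabulate by dose arm including placebo.

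Naming treated participants also settles the denominator. The main analysis set in 7.3 requires primary endpoint data, whereas 5.3 keeps data obtained before withdrawal.

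The cost is a wording amendment, which needs ethics approval under 8.1, and a few tables. One case report form field may be needed: 6.1.1 defines worsening by severity or frequency, and 6.1.2 grades adverse signs and symptoms, but nothing says that baseline symptoms are graded.

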# 3. Trial objective and purpose

#### The primary study objectives are

- (A) To determine the nature of the dose-response (efficacy in terms of cure rate) using oral moxidectin dosages: 2 mg, 4 mg, 6 mg, 8 mg, 10 mg, 12 mg and placebo in a total of 210 adults infected with *S. stercoralis* (trial A: DF study).
- (B) To determine if the efficacy in terms of cure rate of an oral single optimal dose of moxidectin (8 mg based on the outcome of (A)) is non-inferior to the standard dose of a single oral ivermectin application (200 μg/kg), in 350 infected adults in two settings. The non-inferiority margin is set to 10%-points (trial B: parallel group study).

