#### 4.4. Measure to minimize bias

Study participants eligible for treatment will be randomly assigned to one of the seven treatment arms (trial A: DF study) or to one of the two treatment arms (trial B: parallel group study) using a computer-generated stratified by 3 levels of baseline infection intensity (light  $\geq$ 0.4 (trial A) or 0.1 (trial B) – 1 LPG, moderate >1-10 LPG and heavy >10 LPG), block randomization code. The random allocation sequence with varying random blocks of 7 or 14 (trial A) and 2 or 4 (trial B) will be provided by a statistician not involved in enrolment, treatment, and data collection. Stratification will guarantee similar proportion of participants with different infection intensities in all treatment arms. The number of light vs moderate vs. heavy infections, however, are not expected to be equal in each arm, depending on the distribution of infection intensity in the recruited cohort. The codes will be held in a locked cabinet at the Swiss Tropical and Public Health Institute. A copy of this code will be kept in a sealed envelope by one of the co-investigators (will only be opened in emergency situations, determined by the principal investigator upon consultation with the co-investigators). The blinding will be maintained throughout the trial until data entry and processing are complete and the data have been verified. Following release of the final data, the randomization codes will be released.

In previous studies [36] we have observed moderate cure and larvae reduction rates in placebo treated children which are in most cases likely due to the imperfect sensitivity of anthelminthic diagnostics. Participants treated with placebo will be treated at follow up (4 post treatment) with ivermectin (200  $\mu$ g/kg). This treatment delay does not cause noteworthy harm.

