# 8. Duties of the investigator

## 8.1. Investigator's confirmation

This trial will be conducted in accordance with the protocol, International Conference on Harmonisation Good Clinical Practice E6 (ICH-GCP E6 (R2)) and the current version of the Helsinki Declaration.

All protocol modifications must be documented in writing and implemented only with ethical approval. A protocol amendment can be initiated by either the sponsor-investigator or any investigator. The investigator will provide the reasons for the proposed amendment in writing and will discuss with the Sponsor-Investigator. Any protocol amendment must be approved and signed by the Sponsor-investigator and must be submitted to the appropriate Independent Ethics Committee (IEC) for evaluation and approval, in accordance with local requirements, and to regulatory agencies if required. Approval by IEC must be received before any changes can be implemented, except for changes necessary to eliminate an immediate hazard to trial subjects, or when the change involves only logistical or administrative aspects of the trial, e.g. change of telephone number(s).

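### Trial B is decided on an unstratified Wald interval whose one-sided error can run slightly above 2.5%; a score interval, preferably stratified as randomised, corrects this for about 2 points of power

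*Combined protocol and SAP*

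**What the plan says.** Section 7.3 of the combined protocol and SAP states for trial B: "The 95% confidence interval of the differences in CRs will be estimated using the standard formula". The formula that follows is the difference in crude cure rates plus or minus a normal quantile times the root of the summed squared standard errors of the two arms. It has no stratum term. Moxidectin is declared non-inferior if the lower limit exceeds -0.1. The per-protocol analysis in the same section changes the population, and no different interval is given for it.

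Section 4.4 describes a randomisation code that is "computer-generated stratified by 3 levels of baseline infection intensity" (light, moderate, heavy).

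Section 7.2 sets the error standard, "at the 95% confidence interval (equivalent to the 97.5% lower confidence bound", and the planning rate: "We assume a similar true CRs for moxidectin and ivermectin of 89"%. It derives 154 evaluable per arm for 80% power and enrols 175 per arm to allow for 10% loss.

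**The concern.** One interval decides trial B. The Wald interval is known to run somewhat liberal for proportions well above one half, and the cure rates planned here are near 90%. If its true one-sided error exceeds 2.5%, a drug exactly 10 points worse is declared non-inferior more often than 7.2 promises. Separately, the analysis does not use the factor on which randomisation is stratified, so it is natural to ask whether that omission adds to the problem or offsets it. What is at stake is a borderline verdict, where the choice of interval alone could settle the claim.

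**Working it through.** **Inputs.** From 7.2: cure 89% in both arms, one-sided 2.5%, 80% power, 154 evaluable and 175 enrolled per arm, 10% loss. From 7.2 and 7.3: margin 10 points. From 4.4: three strata, 1:1 allocation in small blocks. Section 7.3 does not define the standard errors; they are read as √(CR(1-CR)/n). Stratum shares and stratum cure rates are not in the documents, so those below are assumptions.

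**1. The plan's own figure.** n = (1.96 + 0.8416)² × 2 × 0.89 × 0.11 / 0.10² = 153.7, so 154 per arm, as stated. Expected evaluable: 175 × 0.9 = 157.5; 157 is used below.

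**2. Exact error and power without stratum effects.** All binomial outcomes were enumerated. Error is taken at a true difference of -10 points. Score means the unstratified Miettinen-Nurminen interval.

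| Evaluable per arm | Ivermectin cure | Wald error | Score error |
|---|---|---|---|
| 157 | 85% | 2.63% | 2.49% |
| 157 | 89% | 2.70% | 2.49% |
| 157 | 95% | 3.16% | 2.37% |
| 154 | 89% | 2.74% | 2.37% |

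Power at 89% in both arms: Wald 80.5% and score 77.7% at 154; Wald 81.2% and score 79.1% at 157. At 157 the gap is 81.2 - 79.1, about 2 points, so the two intervals disagree in roughly 1 trial in 50.

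**3. What ignoring the strata does.** Assume shares of 40/40/20% and cure of 96/89/75% on ivermectin (mean 0.4×96 + 0.4×89 + 0.2×75 = 89%), with moxidectin 10 points lower in each stratum.
- Variance term used by the crude formula: 0.89×0.11 + 0.79×0.21 = 0.0979 + 0.1659 = 0.2638.
- Average within-stratum variance: 0.0920 + 0.1600 = 0.2520.
- Ratio of standard errors: √(0.2638/0.2520) = 1.023 in large samples, and 1.016-1.019 by simulation.

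The planned standard error is thus about 2% too wide, which offsets the liberal Wald form.

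**4. Simulated one-sided error at 89% overall** (600,000 runs; fixed stratum sizes 63/63/31 per arm, then 350 enrolled with random 10% loss).

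| Assumed stratum cure | Planned Wald | Stratified Wald | Stratified score |
|---|---|---|---|
| 89/89/89% | 2.69%, 2.64% | 2.74%, 2.72% | 2.46%, 2.41% |
| 92/88/85% | 2.67%, 2.64% | 2.77%, 2.75% | 2.45%, 2.42% |
| 96/89/75% | 2.42%, 2.49% | 2.81%, 2.84% | 2.42%, 2.47% |

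Other stratified score results: 2.3-2.5% for overall cure of 85-95%, and 2.2-2.4% with unequal stratum differences (assumed -5/-10/-20 points). Without the N/(N-1) factor, a separate set of runs over similar patterns gave 2.34-2.56%.

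**5. Power of the stratified score interval at 89% in both arms.** 77.8-79.1% at 154 and 78.7-79.8% at 157 over these three patterns.

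**6. A borderline result.** Moxidectin 135/157, ivermectin 139/157; difference -2.55 points.
- Wald: -0.0255 - 1.96 × √(0.8599×0.1401/157 + 0.8854×0.1146/157) = -0.0255 - 1.96 × 0.0376 = -9.92 points (non-inferior).
- Unstratified score: -10.14 points (not shown).
- Stratified score, assumed strata 63/63/31 per arm: cures 61/55/19 against 62/57/20 give -9.90; cures 54/54/27 against 56/56/27 give -10.16.

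**The case against.** The strongest reply is that the plan is close to adequate. The excess at 89% is 2.70 - 2.50 = 0.20 points. Where the strata are strongly prognostic, which is the case that gives stratified analysis its purpose, the planned interval has the same error as the proposed one (2.42% for both, or 2.49% and 2.47%), and the proposal then costs about 2 points of power with no gain in error. All of this stands. It also stands that the plan's method meets its 80% power target at 154 per arm while the replacement falls slightly short.

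What the reply does not remove is that the planned error depends on stratum effects and cure rates that the documents do not give and that cannot be known beforehand. The Miettinen-Nurminen interval, stratified or not, stayed at or below 2.5% in the scenarios of steps 2 and 4.

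A reader might infer more than this:
- *That leaving out the strata inflates the error.* It does the opposite (step 3).
- *That the borderline example proves a reversal under the stratified method.* It shows sensitivity to the Wald form only; the stratified bound falls on either side of -10 according to how cures are spread over the strata.
- *That stratifying buys power.* The stratified and unstratified score intervals have nearly equal power.

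**Conclusion.** The point holds as a minor one. The planned Wald interval does not quite give the 97.5% lower bound stated in 7.2 when intensity is weakly prognostic: exact error is 2.70% at 89% cure and 157 per arm, and 2.6-3.2% for an assumed ivermectin cure of 85-95%. With strongly prognostic strata the excess vanishes. The exact figures rest only on the planning values, the reading of the standard errors and the stated range of cure rates. The stratified figures (error about 2.2-2.5%) also rest on assumed stratum shares and cure rates. The documents do not support calling the trial invalid or too small. Whether the two countries have separate randomisation lists is a different question and does not bear on this conclusion.

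**What to change.** In 7.3, replace the trial B formula with wording such as: *The 95% CI for the difference in cure rates is the Miettinen-Nurminen score interval (with the N/(N-1) factor), stratified by the three randomised intensity levels with Mantel-Haenszel weights.* Keep the -10-point margin and the decision rule, and report the planned Wald interval as a sensitivity analysis.

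Add a rule for merging a sparse heavy level with the moderate level, fixed on pooled counts before unblinding. Section 4.4 leaves room for this: "The blinding will be maintained throughout the trial until data entry and processing are complete and the data have been verified". A threshold of 20 evaluable in both arms combined was tested; it is a judgement, and merging changed error by at most 0.02 points and power by at most 0.1 points.

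Do not stratify while keeping Wald variances: that gives 2.7-2.8% at 89%. The unstratified Miettinen-Nurminen interval is an acceptable simpler alternative, since it alone repairs the demonstrated error (2.49% at 157 per arm).

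Cost: power at 89% in both arms falls by about 2 points, to about 78-79% at 154 and 79-80% at 157 per arm. Section 7.2 should restate the power for the new interval; no larger trial is asked for. The change needs an amendment, because 8.1 says "All protocol modifications must be documented in writing and implemented only with ethical approval".
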